VISIT 1 (6-12 weeks postnatal): Blood taking: at 0hr and 2hr for oral glucose tolerance test. HbA1C, advanced glycation end-products, C-peptide, HOMA-IR, lipid profile, liver function, hsCRP, and IL-6. Questionnaires: Patients will be asked to fill up a series of questionnaires that will cover their health status, diet, physical activity, and quality of life. An optional 10ml of additional blood will be collected for storage for use in future studies regarding the management of recent gestational diabetes.

VISIT 2 (about 4 months postnatal): Blood taking: at 0hr and 2hr for oral glucose tolerance test. HbA1C, advanced glycation endproducts, C-peptide, HOMA-IR, lipid profile, liver function, hsCRP, and IL-6. Patients will be asked to fill up a series of questionnaires that will cover their health status, diet, physical activity, and quality of life. An optional 10ml of additional blood will be collected for storage for use in future studies regarding the management of recent gestational diabetes.

Details of investigations performed:

- Blood taking for: OGTT, blood metabolic markers (C-peptide, insulin, HbA1C, lipid profile, liver function, hsCRP), blood for future research
- Measurements: Height, weight
- Questionnaires:
 - 1) 3-Day food diary,
 - 2) Self-Efficacy to regulate eating habits questionnaire,
 - 3) Self-Efficacy to regulate exercise questionnaire,
 - 4) Health Education Impact (heiQ),
 - 5) RAND-12 health questionnaire,
 - 6) Health Expenditure questionnaire.

Inclusion criteria:

Female aged 21 years and above; Plans to deliver in NUH; Diagnosed with GDM antenatally (between 12-34 weeks gestation) defined using the 2013 World Health Organization criteria;

Has a smartphone and able to independently use a smartphone app; Willing to provide a blood sample; Able to give written informed consent; Able to speak and read English.

Exclusion criteria:

Subjects with type 1 and type 2 diabetes (including suspected cases diagnosed by an abnormal oral glucose tolerance test in the 1st and early 2nd trimesters of pregnancy); Drugs that affect glucose or lipid metabolism; Terminal or life threatening condition; Physical or mental condition that would prevent completion of a majority of study instruments.

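### Do the inclusion window for GDM from 12 weeks and the exclusion of suspected early diabetes make the same woman both eligible and ineligible?

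*Protocol*

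**What the plan says.** Under Inclusion criteria, the protocol requires that a woman be "Diagnosed with GDM antenatally (between 12-34 weeks gestation) defined using the 2013 World Health Organization criteria". Under Exclusion criteria, it removes "Subjects with type 1 and type 2 diabetes" and adds a parenthesis that widens this to suspected cases: "including suspected cases diagnosed by an abnormal oral glucose tolerance test in the 1st and early 2nd trimesters of pregnancy".

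The inclusion window is given in exact weeks and refers to a named diagnostic standard. The exclusion gives its period only by trimester. It prints no glucose value to separate a result that means GDM from one that means suspected type 2 diabetes. No sentence says how the two criteria are to be read together.

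**The concern.** The inclusion window opens at 12 weeks, around where the first trimester gives way to the second, and the exclusion covers abnormal OGTT results from that same stretch of pregnancy. Consider a woman whose GDM was diagnosed by OGTT at 14 weeks. She falls inside the inclusion window. If any abnormal early OGTT makes her a suspected case, she also falls under the exclusion.

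If staff took different views of such women, the make-up of the enrolled population would depend on who did the screening. Two parts of the plan could be touched. The Randomization section counts type 2 diabetes found after delivery within its 15% attrition allowance. The glucose measures, including the OGTT values and HbA1C, are secondary outcomes. Eligibility belongs in the protocol, so the point cannot be put down to a statistical analysis plan that is not at hand.

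**Working it through.** No sample size, power or error rate is involved, and the protocol states no figure that could be reproduced. The check is a comparison of the two criteria plus one small piece of arithmetic.

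**Inputs from the protocol**

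| Item | Inclusion criteria | Exclusion criteria |
|---|---|---|
| Condition | GDM | Type 1 or type 2 diabetes, established or suspected |
| Period | Weeks 12 to 34 | First and early second trimester, no end week |
| Standard | 2013 WHO criteria | An abnormal OGTT, no value given |

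**Size of the possible overlap**

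- Length of the inclusion window: 34 − 12 = 22 weeks.
- End of the early second trimester: not given; assumed to lie between week 16 and week 20.
- Overlap if it ends at week 16: 16 − 12 = 4 weeks, and 4/22 = 18%.
- Overlap if it ends at week 20: 20 − 12 = 8 weeks, and 8/22 = 36%.

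These are shares of calendar weeks. The protocol does not say how many women have an OGTT that early, so they cannot be turned into shares of women. They also treat every early week as contested, which is true only on the broad reading below.

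**The two readings**

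1. *Narrow.* The parenthesis qualifies type 1 and type 2 diabetes. An early abnormal OGTT is how a suspected case of diabetes comes to light; it is not a separate ground for exclusion. A woman classed as having GDM is included and one suspected of type 2 diabetes is not. The criteria coexist.
2. *Broad.* Any abnormal early OGTT makes a woman a suspected case. A woman diagnosed with GDM at 14 weeks then meets both criteria. Exclusion criteria exist to remove women who otherwise qualify, so she is not enrolled. The early part of the inclusion window is then largely idle for women diagnosed by OGTT, but no woman has to be both enrolled and refused.

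The broad reading leaves the stated 12-week start with little purpose, which favours the narrow one. The protocol does not settle the matter expressly.

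**Effect on the trial's conclusions**

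- *Comparison of arms.* The Design section places consent at 36 to 41 weeks, and the Randomization section places allocation after consent. The diagnosis window closes at week 34. Both criteria therefore rest on facts fixed before allocation, and inconsistent screening would bear on both arms alike.
- *Number of screening settings.* Recruitment runs through the GDM consultations of one hospital, and planned delivery there is an inclusion criterion. The protocol gives no ground for expecting differences between sites.
- *Primary outcome.* It is attainment of a target weight about 4 months after delivery. Neither reading changes its definition, the planned 40% against 20%, or the 64 women required per group.
- *Attrition and secondary glucose outcomes.* An effect here would require early-diagnosed women to differ from the rest in glycaemia or in later diabetes. The protocol gives no figure for this, so no size can be attached.

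**The case for a change.** The strongest case for a change is that the protocol never states the narrow reading. The word *suspected* extends the exclusion beyond established diabetes, and the only marker it offers is an early abnormal OGTT. Elsewhere the protocol does print glucose ranges where the category matters: the standard care arm description gives 6.1 to 6.9 mmol/L fasting and 7.8 to 11.0 mmol/L at two hours for postnatal results. No such range accompanies this exclusion. Even on the narrow reading, someone has to decide which results make a suspected case, and a reader of the final report may not know exactly which women were eligible. One added sentence would remove the doubt at almost no cost.

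Much of this stands. The two terms are undefined, and a woman diagnosed soon after 12 weeks could be read either way. What does not stand is the step from unclear to contradictory. It would be too much to say that every woman diagnosed by OGTT in that period satisfies both rules, since this holds only on the broad reading. The lack of a printed threshold does not prove that screening staff lack a dividing line either: GDM is defined by a named external standard, whose content cannot be checked here. Those who argue for a change also accept that this is a matter of population and consistency rather than of bias between arms, and that no effect on the weight outcome has been shown.

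**Conclusion.** The wording is looser than it should be, but no change to the plan is called for. It is a gap that the clinic can fill sensibly: classify each woman as having GDM or as a suspected case of diabetes, and let the exclusion prevail where it applies. Followed in that way, the plan contains no wrong figure, no bias between arms, no loss of power and no threat to the conclusion on weight.

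The calendar overlap of 18% to 36% rests on the assumed end at week 16 to week 20, and on the broad reading. The share of women affected is unknown. The conclusion also rests on screening being done before allocation at a single hospital, as the protocol describes. A definition of the abnormal result and an end week would tidy the text, but would only write down a rule that staff must already apply. Which rule that should be is a clinical matter on which this review takes no position.
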